#### 6.4 Study Drug Storage and Accountability

For on-site preparation and dispensing of the study drugs, the following procedures will be followed. The investigational drug (IDS) pharmacist of record will: maintain adequate records confirming receipt, expiration dates, or other disposition information on the investigational drug; they will record the name of the individual to whom the drug is shipped, date, quantity, and batch number. They will secure the drug in a locked storage area and monitor to ensure proper storage conditions; they will also complete regular inventory to assure accurate indication of stock on hand, as well as proper recording of stock received, dispensed, and returned. For the 24 patients enrolled for open label pharmacokinetic studies, the pharmacist will generate a label prior to dispensing the study drug, including the date dispensed, quantity and expiration information, drug strength and dose; they will affix the label to the dispensed drug. Pharmacist will generate a label prior to dispensing the study drug, including the date dispensed, quantity and expiration information; they will affix the label to the dispensed drug; they will record but not disclose on the label the drug strength and dose. For dispensing and drug disposition recording,

they will record the date dispensed, patient initials or other identifiers, drug treatments, quantity dispensed, initials of dispenser, date and amount of patient returns documented in study records (i.e., returned drug that cannot be re-dispensed). Filing and all drug documentation will occur within study records and IDS logs. During the infusion, the ketamine will be stored in a lockbox and all Magee standard of care procedures for the safety of controlled substances will be in place for the use of ketamine from the start of infusion through the end of the infusion in the postpartum unit.

#### 6.5 Prohibited Medications

Medications that will not be permitted prior to or during subject participation in the study are as follows:

- Oral antihypertensive medications (exclusion: hypertensive disorders of pregnancy)
- Intravenous magnesium (exclusion: pre-eclampsia with severe features)
- Ketamine, phencyclidine, psilocybins, or any other psychedelics (exclusion: ketamine or PCP abuse)
- Lithium, valproate, carbamazepine, lamotrigine, haloperidol, chlorpromazine, fluphenazine, aripiprazole, clozapine, or other typical or atypical antipsychotic medications (exclusion: schizophrenia or psychosis)

#### 6.6 Rescue Medications

Rescue antiemetics will be provided for patients reporting nausea or vomiting. The following medications will be used to treat nausea or vomiting at the time of patient reporting these symptoms:

- Ondansetron 4mg IVP p.r.n. nausea or vomiting or
- Dexamethasone 4-6mg IVP p.r.n. nausea or vomiting
- After a total of two doses of ondansetron or dexamethasone, additional rescue antiemetics will be given at the full discretion of anesthesiologist

# 7 Research Activities

Figure 1 (section 1.1) illustrates all encounters for measurements at the preoperative baseline, during the intraoperative period, ketamine infusion period, in the postpartum hospital stay (or until patient discharge), and the 1- to 12-week assessments of pain and depression. Study procedures will begin at enrollment pre-operatively, continue during the ketamine infusion, and hospital post-operative stay, continue weekly in the postpartum period, and end at 12-weeks postpartum.

Information collected at baseline includes maternal demographic information, prenatal pain and depressive symptomology, concurrent acute pain, and covariables such as demographic characteristics, and perceived stress. EPDS is completed twice, at least 1 week apart, prior to delivery. The baseline measures are repeated weekly in the postpartum period until 12-weeks postpartum.

During the ketamine infusion, blood samples will be taken at 1-, 6-, 10-, & 12-hours post-infusion start, as well as at the time of any adverse side effect report to assess ketamine/metabolite levels at the time of event.

### Baseline (Preoperative) Procedures.

- a. **Demographic Data and Medical History.** Demographic data will be collected through self-reported questions through the RedCap interface. Data from the medical record will be extracted and recorded by trained research associates to be entered into the RedCap interface. Individual surveys are transposed into RedCap for ease of patient use either on a tablet or paper when patients are in person, and via text or email-linked surveys for remote responses. Survey measure timepoints are described in the Appendix.
- b. **Surveys**. Patient-reported measures will occur by validated instruments delivered by paper, tablet (in hospital), or via Mosio text-based interface with data integration via REDCap. Texting and email will be used via patient-preferred cellular phone numbers and email addresses for 12-weekly postpartum assessments. Each weekly assessment will occur within ±3 days of the weekly postpartum date. Each set of patient-reported REDCap surveys, in total, is expected to last between 15- and 20-minutes, except for the postoperative timepoints which are expected to take less than 15-minutes to complete. Specific surveys and timeline of surveys will be as follows and as indicated in Table 1 and Figure 1.

### **Intraoperative Procedures:** Day of Surgery

Standardized Surgical, Anesthesia and Analgesia Protocols

Surgical personnel role will be recorded (e.g., titles such as private vs faculty obstetricians, resident, or physician assistant). Standardized spinal anesthesia and intraoperative medications will be as follows. Intraoperative medications include current clinical standards of prophylactic phenylephrine infusion to reduce hypotension and related intraoperative nausea/vomiting; ondansetron at the time of delivery for postpartum nausea/vomiting prophylaxis; and ketorolac 15-30 mg at the time of facial closure. Rescue analgesia and antiemetics will follow our existing clinical protocols.

*Spinal anesthesia medications*: bupivacaine 0.75% 1.6mL with fentanyl 10-15mcg and morphine 100-150mcg.

#### Co-medications:

- Per clinical routine, prophylactic phenylephrine infusion at 0.5 mcg/kg/min (37.5mL/hr at standard concentrations) will be started at the beginning of spinal anesthesia induction and discontinued at the time of delivery.
- Supplemental vasopressor boluses are delivered at the full discretion of the managing anesthesiology team.
- Ondansetron 4mg IVP for PONV prophylaxis
- Dexamethasone 4mg IVP for PONV prophylaxis unless contraindications
- Acetaminophen 1000mg either orally pre-operatively or IVPB at facial closure

# • Ketorolac 15-30mg IVP at facial closure

Rescue intraoperative antiemetic: Ondansetron 4mg IVP as a rescue dose as needed x1 dose; dexamethasone 4-6mg IVP as needed x1 dose; after this, additional rescue antiemetic can be given at the full discretion of the managing anesthesia team.

# Postpartum Analgesia Protocol

Postpartum analgesia protocols will be aligned with routine clinical practice at UPMC Magee-Womens Hospital. Specifically, ketorolac 30 mg IV q6h x24 hours (total of 4 doses) will be administered. After all doses of ketorolac have been given, ibuprofen 600mg q6h x24 hours will be delivered, not to be given within 6 hours of ketorolac. Acetaminophen 500-650mg q4h no more than 4000mg q24hr will be given with the first dose given on postoperative day 0. For severe breakthrough pain rated 7-10 on VAS, the Investigator will be called to assess the need to order oxycodone 5-10mg if necessary, as needed for severe breakthrough pain. The Investigator may also assess the need for parenteral rescue agents, namely hydromorphone.

### Discharge Analgesia Regimen

Consistent with current routine clinical practice at UPMC Magee, subjects will be discharged with a prescription for oxycodone 5-10mg q6h #12-20 p.r.n. severe pain. Adjustments to this regimen will be made on an individual basis based on prescriber and institutional practice changes that may arise.

# Surgical case reports.

Surgical elements will be collected from surgeons as well as data abstraction from the medical record (Table 3). Surgeons will complete the Surgeon Operative Survey (Table 2) described below:

# Table 2. Surgical Operative Survey

# Surgeon/Obstetrician Operative Survey

- 1. Reason for Cesarean Delivery
- 2. Type of Skin Incision
- 3. Type of Uterine Incision
- 4. Dissection type and inclusion of rectus
- 5. Uterine exteriorization
- 6. Bladder Flap
- 7. Any unanticipated surgical challenges?
- 8. Please rate difficulty of delivery
  - (0-10 numeric rating scale, 0 is no difficulty, 10 is the most difficult imaginable)
- 9. Please rate difficulty of overall surgery (0-10 numeric rating scale, 0 is no difficulty, 10 is the most difficult imaginable)
- 10. Please rate degree of adhesive disease (0-10 numeric rating scale, 0 is no adhesive disease, 10 is the most adhesive disease imaginable)
- 11. Please rate degree of difficulty of fetal extraction. (0-10 numeric rating scale, 0 is no adhesive disease, 10 is the most adhesive disease imaginable)
- 12. Were there any unanticipated surgical challenges encountered? (yes/no)
- 13. Did you make any intraoperative consultations to other surgeons? (yes/no)
- 14. What materials were used for Facial and Skin closure.

Table 3. Surgical data abstraction from the medical record

Element	Where to find in EHR
Duration of surgery (min)	Cerner Surginet Operative Report
Surgical assist role (resident, physician assistant)	Cerner Surginet Operative Report
Surgical attending role (private vs faculty)	Cerner Surginet Operative Report
Infant weight (grams)	Cerner Surginet Operative Report
Apgar score 1 minute (integer 0-9)	Cerner Surginet Operative Report
Apgar score 5 minutes (integer 0-9)	Cerner Surginet Operative Report
Estimated blood loss (mL)	Cerner Surginet Operative Report Cerner SA Anesthesia Record
Total intravenous fluids administered (mL)	Cerner SA Anesthesia Record
Total urine output (mL)	Cerner SA Anesthesia Record
MME Opioid use in postpartum days 1-3	Cerner SA Anesthesia Record

# Ketamine Infusion, Side Effect Measures, and Plasma Sampling Procedures.

Preoperative weight and vital signs will be measured, and baseline inventories completed (Figure 1). After delivery, cord clamping and declaration of clinical stability by the anesthesiologist (approximately 5-15 minutes after delivery, ± 30 minutes), a loading infusion of ketamine 0.05 mg/kg/hr will begin for the first 3-patients in the study. Vital signs and Richmond Agitation Scale (RASS), and self-reports of side effects will be measured 15, 30, and 60 minutes (±10 minutes) after infusion start, and at 4-8-10-12-16-24- hours (±30 minutes) after infusion start. Plasma samples will be collected at 1-6-, 10- and 12- hours (±30 minutes) after infusion start via an indwelling IV catheter to facilitate ease of access. Plasma samples at 1-6-, 10- and 12- hours after infusion start will be used to calculate Cmax, AUC, and Css and to correlate DLTs with these PK parameters. Any report of adverse events or side effects will trigger a blood draw for analysis and correlation of these symptoms to plasma levels of ketamine. All assessments have been timed to coincide with timing intervals of typical post-CD clinical care interventions. Patient dosing after the first three patients will proceed based on the MTD protocol in Section 1.1.

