# Protocol Overview.

Patients will respond to surveys prior to and following cesarean delivery regarding their current pain and mood. Patients will begin study procedures in the third trimester of pregnancy, within approximately one week of scheduled cesarean delivery, until 12-weeks postpartum.

Preoperative weight and vital signs will be measured, and baseline inventories completed (Figure 1; refer to section 1.1). After delivery, cord clamping and declaration of clinical stability by the anesthesiologist (typically~5-15 min after delivery; ±30 minutes), a loading infusion of ketamine 0.05 mg/kg/hour will begin for the first 3-patients in the study. Vital signs and side effect symptomology will be measured 15, 30, and 60 minutes (±5 minutes) after infusion start, and at 4, 8, 10, 12, 16, and 24 hours (±30 minutes) after infusion start. Plasma samples will be collected at 1, 6, 10, and 12 hours (±30 minutes) after infusion. Any report of adverse events or side effects will trigger a blood draw for analysis and correlation of these symptoms to plasma levels of ketamine within the 12-hour infusion. All assessments have been timed to coincide with timing intervals of typical post-CD clinical care interventions. Patients dosing after the first three patients will proceed based on the MTD protocol in Figure 2; refer to section 1.1.

MTD dosing protocol.

A loading dose and maintenance infusion strategy will be used (Figure 2; in section 1.1). MTD to be tested will focus on the initial loading dose used to achieve a higher plasma concentration in a brief period. Ketamine dose will not exceed sub-anesthetic ranges (≤0.2mg/kg/hr). The maintenance rate of 0.05mg/kg/hr is based on our preliminary data suggesting tolerability, and on data suggesting that this rate might yield adequate plasma concentrations necessary for the treatment of depression. The first set of 3 patients will receive a loading infusion of ketamine 0.05 mg/kg/hr for the first data. The decision to escalate the loading infusion dose, enter 3 more at the same level, or stop, will not occur until 3 patients complete the 0.05 mg/kg/hr protocol. A **DLT** event is defined in section 3.4.1.

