#### 5.4 Recruitment Methods

The current process for research recruitment is that the research anesthesia team will review charts for all patients presenting for cesarean delivery or who are likely to present for a cesarean delivery in the labor and delivery rooms. Prenatal records will indicate patients planning not to breastfeed. During prenatal anesthesiology evaluations, the anesthesiology team will identify patients who are including ketamine infusion as part of their pain management care. Research staff will contact patients to explain the availability of the study to the patient meeting eligibility criteria.

Additional methods of recruitment include directly approaching potential subjects (in-person), the use of Email/Listserv/Electronic Mailing List, use of Flyers/Posters or Brochures in provider offices and clinics, use of Pitt+Me university research registry portal, and patient/participant referrals.

Patients will be eligible if they are receiving ketamine as part of their clinical care, and these typically include patients with a history of complex pain, history of chronic pain with or without treatment, current everyday smokers, patients with opioid or substance use disorder, and patients who have a documented history of treated or untreated anxiety, depression, or trauma.

Eligible patients will be notified of their eligibility to participate in the study by clinical and research staff. Should the patient wish to hear more, the study coordinator will discuss study participation. Questions will be answered, and time will be afforded to patients per the Informed Consent Procedures outlined, to minimize risks of coercion or undue influence.

Upon completion of the baseline inventories and the ketamine infusion and blood collection, patients will receive a payment of \$750 (see Appendix 4 for payment details). Upon completion of the postpartum weekly surveys, payments of up to \$150 will be made at both 6- and 12-weeks postpartum.

*In-Hospital Encounter*Baseline inventories

Complete infusion and all blood draws	\$ 750.00
Postpartum Encounters	
Complete all weekly surveys @ \$25.00/week	
Complete weekly surveys for 6 weeks	up to \$150.00
Complete weekly surveys for weeks 7-12	up to \$150.00
Grand Total	\$ 1,050.00

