#### Side Effect Acceptability Ratings.

Our existing and previously tested **digital diary** will automate alerts for questions about side effects after infusion start at 15-, 30-, 60- minutes, and every 4 hours in the first 24 hours after infusion start (Figure 1, section 1.1). The diary has been tested and used by our group in previous work; alerts coincide with RASS assessments and similar timing of clinical assessments for routine CD nursing care and monitoring (i.e., is not more burdensome or intrusive to patients than routine clinical post-CD care). The digital diary will assess side effects

(i.e., dizziness, lightheadedness, bad dreams, nausea, vomiting, itchiness, and hallucinations: all dichotomous outcomes). Any positive response to any item will trigger the subject to rate their acceptability of side effects in the following way. Patient-reported acceptability is defined based on theoretical framework of acceptability and focused on constructs of *Burden* ("Would experiencing side effects keep you from participating in this intervention (ketamine) again?" yes/no) and *Affective Attitude* ("Based on your experience with this medication, would you be willing to participate in this intervention (ketamine) again?" yes/no). Either a negative response to Attitude, or a positive response to Burden, will define patient unacceptability.

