Appendix 2 – Schedule of Perinatal, Surgical, and Infusion-Specific Research Activities

			Study Visit# 1; Day 0—Delivery/Cesarean Surgery -24 hours post-surgery												
Screening & Baseline Measures	screening seline ures	Presurgical Intake T-1 hour If not completed at baseline	Cesarean Surgery	Ketamine Infusion 15-45 minutes Post	12-hour Ketamine Infusion 12-hour post-infusion								fusion		
			Cesarear		15 Minutes	30 Minutes	Hour 1	Hour 4	Hour 6	Hour 8	10Hour	Hour 12	Hour 16	Hour 20	Hour 24
Informed consent	Х														
Demographics and Medical History (inc. Opioid use in hospital)	Х	Х													
Concomitant medication review	Х	X													
Administer study intervention				X											
Maternal Plasma Samples a							Χ		Χ		Χ	X			
Adverse event review b				X											X
Surgical operative survey				Х											
Pain Intensity	Х	X													
Pain Unpleasantness	X	X													
PROMIS-PI	X	X													
EPDS	Х	X													
PSS	X	X													
SF-MPQ	Х	X													
RASS b					Х	Χ	Χ	Х		X	X	Х	Х	Χ	X
Patient Vitals b		X		Х	X	Х	Χ	Х	Х	Χ	Χ	Х	Χ	Χ	X
LSD Short b					Х	Х	Х	Х		Х	Х	Х	Х	Х	Х
Side Effect Diary and Patient Acceptability b					Х	Х	Х	Х		Х	Х	Х	Х	Х	Х

<sup>a Maternal Plasma Sampling includes analysis of Ketamine, ketamine metabolites (Nor-Ketamine & DKNK), Ketamine R- & S-isomers, cortisol, prolactin, and CYP3A and CYP2B6 enzymes

b Adverse Events will result in collection of RASS, LSD short form, Patient vitals, Patient Acceptability ratings, and Maternal plasma sampling at any point between infusion start (t = 0) to 24-hours post-infusion start. LSD score of >8 will trigger a notification to staff and investigator to prompt bedside evaluation.

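### RASS, the LSD short form and the side-effect diary have no pre-infusion assessment, so side-effect rates and symptom-to-plasma correlations mix pre-existing with post-infusion symptoms

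*Combined protocol and SAP*

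**What the plan says.** Three places in the text set the first symptom assessment. Section 4 (Protocol Overview): "Vital signs and side effect symptomology will be measured 15, 30, and 60 minutes (±5 minutes) after infusion start". Section 7 (Ketamine Infusion, Side Effect Measures, and Plasma Sampling Procedures): "self-reports of side effects will be measured 15, 30, and 60 minutes (±10 minutes) after infusion start". Section 7 (Side Effect Acceptability Ratings): the digital diary "will automate alerts for questions about side effects after infusion start at 15-, 30-, 60- minutes".

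In Appendix 2 the RASS, LSD short form and diary rows are first marked in the 15-minute column, with nothing at screening, presurgical intake, surgery or infusion start. Collection triggered by an adverse event is also confined to the period after the pump starts: "at any point between infusion start (t = 0) to 24-hours post-infusion start". Vital signs do have an entry at presurgical intake. The baseline inventories cover pain, depression and stress.

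Before ketamine, each patient receives a spinal containing "bupivacaine 0.75% 1.6mL with fentanyl 10-15mcg and morphine 100-150mcg". A prophylactic phenylephrine infusion "will be started at the beginning of spinal anesthesia induction and discontinued at the time of delivery". Ketamine follows about 5 to 15 minutes after delivery (±30 minutes), once the anesthesiologist has declared the patient stable.

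Any positive diary item prompts an acceptability rating. Section 12.4 reports the ratings for each side effect as numbers and percentages. Any report of a side effect also triggers a blood draw, so that symptoms can be correlated with ketamine levels.

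**The concern.** The diary asks about nausea, vomiting, itchiness, dizziness, lightheadedness, bad dreams and hallucinations; RASS grades sedation. Several of these can be present in a patient who has just had a spinal with opioids and a cesarean delivery, before any ketamine. The protocol itself links intraoperative hypotension with nausea and vomiting, and it schedules antiemetic prophylaxis. That spinal opioids can also cause itching or sedation is general clinical knowledge; the documents give no rates.

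Neither the diary rule nor Section 12.4 asks whether a symptom is new or worse since the infusion began, and the design is open-label with no control arm. A symptom carried in from the operating room and reported at 15 minutes is therefore tabulated in the same way as one that starts during the load. At stake is how far the secondary endpoint, side-effect acceptability, and the symptom-to-plasma analysis can be interpreted.

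**Working it through.** The plan states no figure that depends on this point, and Section 12.2 says that no power calculation was done. There is nothing to reproduce, so the check is a reading of the schedule followed by three short calculations.

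**1. Can the first reading fall before the drug?** No. Under the Section 7 window it falls between 15 − 10 = 5 and 15 + 10 = 25 minutes after start. Under the Section 4 window it falls between 15 − 5 = 10 and 15 + 5 = 20 minutes. (The two windows differ and should be reconciled, but the conclusion is the same.)

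**2. Can the 15-minute reading serve as a baseline?** No. The one-hour load is the variable under test. At 15 minutes, 15/60 = 25% of it has been given; across the Section 7 window the share runs from 5/60 = 8% to 25/60 = 42%. The same step shows the problem for the plasma analysis: a pre-existing symptom reported early in the load is paired with an early ketamine level to which it may be unrelated.

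**3. How much does one misattributed patient move a reported rate?** 1/3 = 33 percentage points in a cohort of 3, 1/6 = 17 in a cohort of 6, and 1/12 = 8 if all 12 patients are pooled.

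**4. How often would a cohort include a patient with a pre-existing symptom?** Assume that a share p of patients has at least one diary symptom at infusion start; the documents give no value. The chance of at least one such patient among n is 1 − (1 − p)^n.

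| p (assumed) | n = 3 | n = 6 |
|---|---|---|
| 10% | 27% | 47% |
| 20% | 49% | 74% |
| 30% | 66% | 88% |

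These are chances that a symptom is present. They are not DLT rates.

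**5. Can the route to the MTD be sized?** Under Section 3.4.1 a side-effect DLT requires complete infusion cessation, and escalation stops at 2 DLTs in 3 to 6 patients. The chance of stopping at one dose level is 1 − [(1 − q)^3 + 3q(1 − q)^5], where q is the total DLT probability. Write q = 1 − (1 − k)(1 − b), with k from ketamine and b from pre-existing symptoms, taken as independent. For k, use 12.5% purely as an illustration: it is the 1/8 in Section 6.3 whose infusion rate was below 0.05 mg/kg/hr because of side effects, and it is not a DLT rate. Let b = p × c, where c is the unknown share of symptomatic patients whose infusion is stopped for that symptom. Hold p at an assumed 20%.

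| c (assumed) | b | q | Chance of stopping at the level |
|---|---|---|---|
| 0 | 0% | 12.5% | 13.8% |
| 1 in 10 | 2% | 14.25% | 17.1% |
| 1 in 2 | 10% | 21.25% | 31.9% |
| all | 20% | 30% | 50.6% |

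The result depends almost wholly on c, for which the documents give nothing.

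**The case against.** The strongest reply is that the plan already has several aids to attribution:

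- Section 10 grades adverse events for relatedness, weighing timing, other drugs and response to withdrawal.
- A plasma sample is drawn when a side effect is reported.
- Table 1 (Section 6.3) provides holds and dose reductions, which act as a dechallenge.
- Four dose schematics are planned.
- An anesthesia provider is present for the first 30 minutes (Section 7.4).

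This stands as far as it goes. It would be wrong to infer that a pre-infusion reading is the only possible reference, or that the investigator and DSMB would have nothing to go on. But none of these records whether the symptom was there before the drug, and relatedness grading is not tied to the diary counts or to the DLT definition.

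A second reply is that the endpoint is acceptability: the rating questions name ketamine, and Section 12.4 is descriptive. That is fair, and the plan makes no formal causal claim. Even so, a reader of a table of side effects by percentage will take them as effects of the drug.

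Third, a reader might infer that the LSD cutoff distorts an endpoint, because one entry route typically includes "patients who have a documented history of treated or untreated anxiety, depression, or trauma". The documents do not support this. "LSD score of >8 will trigger a notification to staff and investigator to prompt bedside evaluation" is all that the cutoff does; it is neither a listed endpoint nor a DLT criterion, and nothing in the documents says how these patients score before ketamine.

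Finally, a baseline catches only part of the confounding. Ketamine starts soon after delivery, and spinal or surgical symptoms that begin after the pump starts would still look new. This limitation stands.

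**Conclusion.** The gap is real: no RASS, LSD short form or diary reading is scheduled before infusion start, and nothing in the counting rule separates old symptoms from new ones. The consequence is limited interpretability of the Section 12.4 side-effect percentages and acceptability ratings, and of the symptom-to-plasma correlation. With cohorts of 3 to 6, a single patient moves a rate by 17 to 33 percentage points.

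The tempting stronger reading is that the MTD is biased downward by a material amount. The documents do not support it. A pre-existing symptom becomes a DLT only if it is rated unacceptable, or persists as sedation, nausea or vomiting, through the Table 1 steps until the infusion is stopped; several of those steps leave discontinuation to investigator discretion. An effect on the MTD is possible, and its direction would be downward, but the table in step 5 shows that its size rests on assumed values. The 27% to 88% in step 4 should not be quoted as DLT probability or MTD bias. The blood-pressure and heart-rate DLT criteria are not affected.

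This is a cheap and worthwhile improvement, not a flaw that invalidates the design.

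**What to change.** - **Appendix 2 and Sections 4 and 7:** add RASS, the LSD short form and the diary symptom items once, after delivery and before the pump starts. Omit the acceptability questions at that time, since they ask about ketamine. State the timing explicitly: the existing infusion column does not make clear what precedes the start of the pump.
- **Section 12.4:** report each side effect two ways, as all reports and as reports new or worse than the pre-infusion assessment. Report change in LSD score descriptively.
- **DLT review:** give the pre-infusion record to the investigator and the DSMB.
- **Limitations:** leave the DLT and dose-adjustment rules unchanged. State that the added assessment does not remove any MTD bias and cannot separate spinal or surgical symptoms that begin after infusion start.

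The cost is amendment wording and a few minutes of patient burden in the perioperative period, with instruments already in use.
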